1.0 Objectives

1.1 Study Objectives

Describe the purpose, specific aims or objectives. State the hypotheses to be tested.

Achilles Tendon Ruptures (ATR) are common and permanently affect the function of the lower leg. Regardless of the treatment approach, most patients develop long-term functional deficits, including decreased plantar flexion strength, lower heel-rise height, and altered gait patterns. It is believed that tendon lengthening and calf muscle atrophy, which develop during the first few weeks of recovery, contribute to these functional deficits. The initial development of atrophy is likely caused by reduced loading and muscle activity of the affected leg. However, long-term atrophy may be related to tendon elongation. On the other hand, tendon elongation initially rises during the first few weeks of unloading and slowly reduces, but not wholly, when loading is resumed. However, atrophied calf muscles may need to provide more loading for optimal tendon recovery. Therefore, there seems to be a vicious spiral between tendon elongation and muscle atrophy.

This study aims to evaluate a neuromuscular electrical stimulation (NMES) rehabilitation protocol for Achilles tendon ruptures. Our preliminary data has shown that force applied to the tendon can be modulated using electrical intensity and pad placement. Therefore, NMES can produce significant contraction in the calf muscles and induce controllable, low-magnitude, cyclic loading to the tendon, which cannot be achieved with voluntary muscle contractions. This approach can potentially overcome the limitations of the current rehabilitation protocols.

The results of this study will allow the development and demonstration of the initial feasibility of an NMES protocol for patients recovering from ATR. This protocol may improve lower-leg strength and tendon and muscle properties of patients recovering from an ATR, which can result in improved functional outcomes. NMES technology is widely available in physical therapy and rehabilitation centers. Consequently, NMES can be quickly adopted and incorporated as part of routine care for ATR.

This is the second phase of a three phase study.

1.2 Primary Study Endpoints

State the primary endpoints to be measured in the study.

Clinical trials typically have a primary objective or endpoint. Additional objectives and endpoints are secondary. The endpoints (or outcomes), determined for each study subject, are the quantitative measurements required by the objectives. Measuring the selected endpoints is the goal of a trial (examples: response rate and survival).

The primary outcome of this study is to measure the ability of participants to perform a heel rise at week 12, which is a strong predictor of long-term outcomes.

1.3 Secondary Study Endpoints

State the secondary endpoints to be measured in the study.

Muscle volume, Achilles tendon length and area, steps, and self-reported outcomes VAS (pain), ATRS, FAOS, PAS, adverse events, and compliance to the proposed treatment.

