2.0 Background

2.1 Scientific Background and Gaps

Describe the scientific background and gaps in current knowledge.

For clinical research studies being conducted at Penn State Health/Penn State College of Medicine, and for other non-PSH locations as applicable, describe the treatment/procedure that is considered standard of care (i.e., indicate how patients would be treated in non-investigational setting); and if applicable, indicate if the study procedure is available to patient without taking part in the study.

Achilles tendon rupture (ATR) is a common injury that affects active individuals and has increased 10-fold in the past few decades [1]–[6]. Approximately one out of five patients are unable to return to previous activity levels [7], and two out of three have continued functional deficits seven years after injury [8]. Lower-leg functional deficits include decreased heel-rise height, heel-rise work, concentric strength power, reduced plantar flexion strength [9], and decreased ability of the ankle to absorb load and generate power [10]. These deficits persist beyond 14 years after injury [11]. Poor functional outcomes resulted in 30-40% of athletes not returning to the professional level and those who do have up to a 50% reduction in performance levels [12], [13]. Structural changes in the tendon-muscle unit after ATR are strongly related to deficits in plantarflexion function and altered running and jumping biomechanics 1-6 years after injury [14]. Specifically, ATR results in long-term tendon elongation [15], increased tendon area [16], [17], altered mechanical properties [18], [19], and reduced calf muscle volume [16]. These structural changes rapidly develop over the first weeks of recovery, continue for a few months after injury and change very little after that [20]. Therefore, recent improvements in rehabilitation protocols have focused on including early mobilization and weight-bearing [21]. Although these protocols result in better outcomes [22], patients still develop functional deficits [22]–[26].

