7.1 Study Design

Describe and explain the study design.

This is a randomized clinical trial with two groups: control and stimulation. Participants will be randomly assigned to a NMES (active) treatment or control group in a 1:1 ratio. No stratification factors will be considered in the randomization process based on covariates such as gender, activity, and age. In the stimulation group, subjects will receive standard rehabilitation and NMES will be applied to calf muscles 6 weeks after repair surgery. The pad placement and stimulation parameters will be updated in a weekly basis for the stimulation group. The control group will follow standard rehabilitation and will not receive NMES. For both groups, ultrasound evaluation will be performed at week 6 and 12 weeks after surgery. The primary outcome (heel-rise) will be measured at week 12 after repair. Other outcomes (activity level, pain) will be measured daily for the first 6 weeks after repair.

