7.2 Study Procedures

Provide a step by step description of all research procedures being conducted (broken down by visit, if applicable) including such information as below (where and when applicable); describe the following:

- HOW: (e.g., data collection via interviews, focus groups, forms such as surveys and questionnaires, medical/school records, audio/video/digital recordings, photographs, EKG procedures, MRI, mobile devices such as electronic tablets/cell phones, observations, collection of specimens, experimental drug/device testing, manipulation of behavior/use of deception, computer games, etc.)
- WHERE: (e.g., classrooms, labs, internet/online, places of business, medical settings, public spaces, etc.)

All participants participating will receive a standard rehabilitation protocol. All participants will be randomly assigned to NMES or control (standard of care) for the first 6 weeks after surgery. For the randomization process, a master list with patient codes will prepopulated with randomly assigned treatments (NMES vs control). As recruitment is performed, patients will be assigned a code with the corresponding intervention. The randomization will be performed at a 1:1 ratio between control and stimulation group. The research teams conducting the rehabilitation protocol at the Hershey Medical Center will instruct and evaluate all participants on how they place the electrodes, operate the NMES device (intensity combo II. This is a commercially available, FDA-approved device), and select the parameters to be used (Table 2 and Figure 2). The intensity will be set to the maximum comfortable intensity by the patient. Additionally, the research team will ensure the participants perform the procedure correctly at each weekly visit. The NMES device has an adherence meter to evaluate adherence to the protocol. Self-applied NMES intervention has been successfully used in several studies targeting muscle weakness after major knee surgeries [53], [54].

Table 2. Proposed NMES protocol

Week	Pad Placement	Time (min) x times per day
1	I, II, III	10 x 1
2-3	I, II, III	10 x 2
4-6	IV	20 x 2

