Self-reported diary and outcomes: To evaluate frequency of loading, from the day after surgery, participants will complete a diary (paper or electronic survey via REDCAP) on estimated daily weightbearing load, number of steps/days with a pedometer placed at the hip, and pain on a visual analogue scale (VAS). Although standard of care prescribes no weight-bearing during the first two weeks after repair, patients are active during that period of time. The level of activity (steps), even though does not involve the use of the injured limb, can help explain potential differences in self-reported outcomes, especially kinesiophobia scores. These measurements are not part of the standard of care. Self-reported outcomes will be also collected at weeks 6 and 12: the Achilles tendon Total Rupture Score (ATRS) [56], the Physical Activity Scale (PAS) [57], the Foot and Ankle Outcome Score (FAOS) Quality of Life subscale [58], and the Tampa Scale of Kinesiophobia (TSK) [59], [60]. Patient reported outcomes (ATRS, PAS and FAOS) are part of the standard of care for Achilles tendon rupture.

Single heel-rise tests: The ability of performing a single heel-rise will be evaluated at week 12. The participants will stand on a flat box with the ankle in neutral position and will be asked to perform a single heel-rise. The participants will be classified as being able to perform a one-legged heel-rise if they were able to lift the heel at least 2 cm once while keeping the knee straight [60]. MuscleLab® (Ergotest Technology, Oslo, Norway) measurement system will be used for the evaluations as previously described in our previous study [29]. This will be performed in the physical therapy clinic at [name]. This test is not part of the standard of care for Achilles tendon rupture.

Table 3. Study Procedures for Stimulation and control groups

Week	Procedure
1	Consenting, Randomization, Distribution of diary and activity monitor, Demonstration of NMES (stimulation group only), (in-person visit)
2, 4	Adjustment of NMES (stimulation group only), collection of steps, and diary data. (Visit 2 can be done virtually with a video call, visit four should be done in person.)
6	Ultrasound Imaging, Questionnaires (ATRS, PAS, FAOS, TSK), collection of steps and diary data, Discontinue use of NMES (stimulation group only). (In-person visit)
12	Ultrasound Imaging, Heel-rise test, Questionnaires (ATRS, PAS, FAOS, TSK) (In person visit)

7.2.1 Visit 1 (Week 1).

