Provide a description of what procedures will be performed on visit 1 or day 1 or pre-test in order of how these will be done. If your study only involves one session or visit, use this section only and indicate 7.2.2 as not applicable.

This visit will be scheduled in first week after the surgery. The research team or clinician of the research team will demonstrate the NMES procedure to the participants. The research team will verify that the procedure is applied properly and follows with the protocol. An explanation of the information needed for the diary will also be provided. Participants will take the NMES device (for the treatment group) and the diary home and perform the procedure by themselves. Randomization will be communicated to the patient at this visit. Participants are provided the pedometer at this visit, and instructions on how to use it. The study team will not collect AEs at this visit. The total duration of this visit is estimated to be 45 minutes.

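### No pre-treatment activity level is scheduled, so the activity covariate named in 7.1 and 8.3 has no valid input and some precision on the PAS is lost

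*Combined protocol and SAP*

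**What the plan says.** - **Endpoints.** Section 1.3 names "self-reported outcomes VAS (pain), ATRS, FAOS, PAS" among the secondary endpoints, along with steps.
- **Timing of questionnaires.** Section 7.2 states: "Self-reported outcomes will be also collected at weeks 6 and 12". The set is ATRS, PAS, FAOS and TSK. Table 3 and the visit descriptions (7.2.4, 7.2.5) agree.
- **Visit 1.** Table 3 gives its content as "Consenting, Randomization, Distribution of diary and activity monitor, Demonstration of NMES (stimulation group only), (in-person visit". Section 7.2.1 lists no questionnaire and no recall of pre-injury status. It adds: "Randomization will be communicated to the patient at this visit".
- **Week 6.** Table 3 lists "Ultrasound Imaging, Questionnaires (ATRS, PAS, FAOS, TSK), collection of steps and diary data, Discontinue use of NMES (stimulation group only". Section 7.2 sets the treatment period: "All participants will be randomly assigned to NMES or control (standard of care) for the first 6 weeks after surgery".
- **Early activity data.** Section 7.1 says: "Other outcomes (activity level, pain) will be measured daily for the first 6 weeks after repair". The pedometer is handed out at visit 1, after surgery.
- **Activity as a covariate.** Section 7.1 names activity, with gender and age, as a covariate on which randomisation will not be stratified. Section 8.3 plans a chi-square comparison of the groups on the same three covariates, followed by a Cochran-Mantel-Haenszel test.
- **Analysis of questionnaires.** Section 8.3 gives no between-arm analysis for any of them.

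**The concern.** A covariate used to check balance or to adjust a treatment comparison should be fixed before treatment starts. The plan names activity in that role but schedules no measurement that qualifies. A chi-square comparison of the arms on activity measured during or after NMES would compare outcomes. It would not check balance, and stratifying on such a variable could remove part of a treatment effect.

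Participants are aged 18 to 65 and may have differed widely in activity before the rupture. Randomisation is unstratified, with 25 per arm. Two things are at stake:

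- whether a chance imbalance in pre-injury activity can be seen and allowed for;
- how precisely the week-12 PAS can be compared between arms.

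**Working it through.** **1. Can any scheduled measurement serve as a baseline?**

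| Candidate | When taken | Usable? |
|---|---|---|
| PAS, week 6 | At the visit where NMES stops. The standard protocol in 2.1 has the boot worn until after week 7 | No: post-treatment, and activity is restricted |
| Pedometer steps | From visit 1, in the first week after surgery, while NMES is in use | No: during treatment, under restricted weight bearing, and itself an endpoint in 1.3 |
| Diary weight-bearing | From the day after surgery | No: reflects post-operative restriction |
| PAS at visit 1 | Not scheduled | – |

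One phrase in 7.1 can be read as placing NMES at 6 weeks after surgery. Table 2, Table 3 and 7.2.4 run it through weeks 1 to 6, and this check uses that schedule. The wording should be reconciled.

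**2. Arm sizes.** The plan gives no power figure for the questionnaires. Section 8.2 gives 22 per group for heel-rise, 50% against 85%. The pooled-variance formula for two proportions, one-sided 5% and 80% power, reproduces it:

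[1.645 × √(2 × 0.675 × 0.325) + 0.842 × √(0.25 + 0.1275)]² / 0.35² ≈ 21.1, rounded up to 22.

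With 10% attrition, 22/0.9 = 24.4, rounded up to 25. The two-sided figure is 27. That is a separate matter, and only the arm sizes of 25 and 22 are used here.

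**3. Precision on week-12 PAS.** Let r be the correlation between the recalled pre-injury score and the week-12 score. Neither r nor the SD is in the documents, so r is varied and results are in SD units, treating the score as roughly continuous. Adjustment multiplies the residual variance by 1 − r². The detectable difference d (two-sided 5%, 80% power) solves a noncentral t with noncentrality d/√(1 − r²) × √(n/2) and 2n − 2 degrees of freedom, one fewer with the covariate.

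| r (assumed) | Variance cut | d, 25 per arm | d, 22 per arm | 25 per arm is worth |
|---|---|---|---|---|
| none | – | 0.81 | 0.87 | 25.0 |
| 0.2 | 4% | 0.79 | 0.85 | 25/0.96 = 26.0 |
| 0.3 | 9% | 0.77 | 0.83 | 25/0.91 = 27.5 |
| 0.6 | 36% | 0.65 | 0.69 | 25/0.64 = 39.1 |

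**4. Chance imbalance.** The between-arm difference in a standardised baseline variable has standard error √(2/25) = 0.28 SD. An imbalance beyond 0.3 SD in either direction has 0.3/0.283 = 1.06, a two-sided probability of about 29%. Such an imbalance shifts the unadjusted week-12 difference by r × 0.3: 0.06, 0.09 or 0.18 SD for r = 0.2, 0.3 or 0.6. The half-width of the unadjusted 95% confidence interval is 0.57 SD, so the shift lies well inside the stated uncertainty.

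**The case against.** The strongest case against is that little is lost.

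- **Validity.** Randomisation makes the week-12 comparison unbiased, and the confidence interval already allows for chance imbalance. A reader might infer that a PAS difference would be confounded with pre-injury activity. The design does not support that. This part of the objection stands: the loss is in precision and in the ability to check and adjust.
- **Aim.** A reader might infer that the trial cannot measure the deficit it sets out to treat, because 2.1 says "Approximately one out of five patients are unable to return to previous activity levels". That is one sentence of background. No objective or endpoint in 1.1 to 1.3 concerns return to previous activity. Week 12, about five weeks after the boot comes off, may also be too early for it. This stands too.
- **Analysis.** It is tempting to say that the arms will be compared on raw PAS scores. Section 8.3 specifies no PAS comparison at all, so that cannot be attributed to the plan.
- **Size.** No source supports any value of r. Recall error and activity limits still in force near week 12 could keep it low, and at r = 0.2 the gain is 4% of variance. This stands, and is why the low value is in the range.
- **Other sources.** Section 7.2 calls ATRS, PAS and FAOS standard of care, and the screening questions are in a separate document. A pre-injury value might exist somewhere. The supportable statement is that none is scheduled or assigned a use.

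The objection does not answer the covariate problem. The plan names activity as a covariate twice and schedules no pre-treatment value for it.

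**Conclusion.** The point holds in a limited form. No pre-treatment activity level is scheduled, and neither week-6 PAS nor post-surgery steps can stand in for one. The activity covariate in 7.1 and 8.3 therefore has no valid input, and a chance imbalance in pre-injury activity can be neither checked nor adjusted for.

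The precision lost on week-12 PAS is small if r is 0.2 to 0.3 and material if r is near 0.6. It rests on an assumed r and concerns one secondary endpoint with no stated power. The documents support neither a finding of bias nor a finding that the trial misses its own aim. VAS pain and steps, recorded daily after surgery, are outside the point as endpoints. Low severity; a cheap improvement.

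**What to change.** 1. **Visit 1.** After consent and before the allocation is communicated, have every participant complete the PAS for the period just before the injury. Add this to Table 3 and 7.2.1.
2. **Section 8.3.** Define the activity covariate as this value, with any categories for the Cochran-Mantel-Haenszel test fixed in advance. Add a between-arm analysis of week-12 PAS with the same value as baseline covariate.
3. **Optional.** Report by arm, descriptively, the proportion back at their pre-injury PAS level. Use the value as a covariate for week-12 ATRS and FAOS only if wanted, since nothing in the documents shows that it predicts them.

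The cost is one questionnaire already in the study set, added to an existing visit estimated at 45 minutes, and a short addition to 8.3. That addition has to include the PAS analysis itself, because none is there now. Treatment, visits and sample size do not change. The downside is recall error, which cannot be influenced by knowledge of the arm if the form is completed before allocation is communicated. The trial is unblinded, so a value asked for later would lose that protection.

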2.0 Background

2.1 Scientific Background and Gaps

Describe the scientific background and gaps in current knowledge.

For clinical research studies being conducted at Penn State Health/Penn State College of Medicine, and for other non-PSH locations as applicable, describe the treatment/procedure that is considered standard of care (i.e., indicate how patients would be treated in non-investigational setting); and if applicable, indicate if the study procedure is available to patient without taking part in the study.

Achilles tendon rupture (ATR) is a common injury that affects active individuals and has increased 10-fold in the past few decades [1]–[6]. Approximately one out of five patients are unable to return to previous activity levels [7], and two out of three have continued functional deficits seven years after injury [8]. Lower-leg functional deficits include decreased heel-rise height, heel-rise work, concentric strength power, reduced plantar flexion strength [9], and decreased ability of the ankle to absorb load and generate power [10]. These deficits persist beyond 14 years after injury [11]. Poor functional outcomes resulted in 30-40% of athletes not returning to the professional level and those who do have up to a 50% reduction in performance levels [12], [13]. Structural changes in the tendon-muscle unit after ATR are strongly related to deficits in plantarflexion function and altered running and jumping biomechanics 1-6 years after injury [14]. Specifically, ATR results in long-term tendon elongation [15], increased tendon area [16], [17], altered mechanical properties [18], [19], and reduced calf muscle volume [16]. These structural changes rapidly develop over the first weeks of recovery, continue for a few months after injury and change very little after that [20]. Therefore, recent improvements in rehabilitation protocols have focused on including early mobilization and weight-bearing [21]. Although these protocols result in better outcomes [22], patients still develop functional deficits [22]–[26].

Standard Rehabilitation Protocol: Participants will receive the current standard rehabilitation protocol given at Hershey medical center or any other suggested medical center suggested by their surgeon. Briefly, no weight bearing for the first 2 weeks, followed by partial weight bearing in a cam boot with heel wedges for weeks 3 and 4. Gradual reduction of heel wedges during weeks 5 to 6. After 7 weeks, participants will discontinue the use of a cam boot and progressively transition to full weight bearing.

2.2 Previous Data

Describe any relevant preliminary data.

A recent double-blind study (clinicaltrials.gov NCT01833936) that applied a **one-time session** of NMES (at the moment of surgery) to patients undergoing ATR repair reported trends towards improvement of muscle volume [27]. It is extremely encouraging that a one-time application of NMES resulted in ‘trends’ towards maintaining muscle volume and this provides support that a daily structured NMES protocol would enhance those results. Additionally, the proposed study will evaluate not only muscle volume, but also early structure (tendon length, area and mechanical properties) as functional parameters (heel rise) that have been shown to be predictive of longer term functional outcomes [28], [29].

Relationship between NMES pad position, intensity and force: Pad placement plays an important role in the amount of force generated during NMES. Four placements are considered in this study (Fig. 2). Placements I to III covered small regions of the calf: medial gastrocnemius, lateral gastrocnemius, and soleus, respectively. Placement IV covered all calf muscles. The NMES parameters used are shown in Table 1. 20 healthy subjects (age range 20 to 53) were recruited for this pilot study. Plantar flexion angle had a minor effect on force for placement IV. For the other pad placements, the effect was negligible. The force produced by each

placement increased as a function of intensity until it plateaus (Fig. 3). As expected, pad placement covering small regions of the calf muscle (placements I, II, and III) produced lower forces compared to stimulating all calf muscles (placement IV). Interestingly, placement IV had a sharp increase of force and plateaued at lower intensities compared to the other pad placements. This indicates that it will be easier to tune and produce smaller forces when stimulating smaller regions of the calf muscles. In later stages of healing, pad placement IV can provide larger forces.

Table 1. NMES parameters for patients recovering from ATR.

Hz	PW (μs)	Plantar Flexion
50	300	0°, 10°, 20°, 30°

